	Moderate (N=X)		Severe (N=X)		Moderate (N=X)		Severe (N=X)		Moderate (N=X)		Severe (N=X)	
	N	%	n	%	n	%	n	%	n	%	n	%
Any Medication/Therapy	x	xx	x	xx	x	xx	x	xx	x	xx	x	xx
Protease inhibitors	x	xx	x	xx	x	xx	x	xx	x	xx	x	xx
Polymerase inhibitors	x	xx	x	xx	x	xx	x	xx	x	xx	x	xx
Potential Treatments for COVID-19	x	xx	x	xx	x	xx	x	xx	x	xx	x	xx
Chloroquine/Hydroxychloroquine	x	xx	x	xx	x	xx	x	xx	x	xx	x	xx
Other	x	xx	x	xx	x	xx	x	xx	x	xx	x	xx
Corticosteroids	x	xx	x	xx	x	xx	x	xx	x	xx	x	xx
Other anti-inflammatory drugs	x	xx	x	xx	x	xx	x	xx	x	xx	x	xx
Monoclonal Antibodies Targeting Cytokines	x	xx	x	xx	x	xx	x	xx	x	xx	x	xx
Other Biologic Therapies	x	xx	x	xx	x	xx	x	xx	x	xx	x	xx

N = Number of subjects in the As Treated Population.

n=Number of subjects reporting taking at least one medication in the specified category.

Programming Note: only include medications where the end date is missing (i.e. ongoing) or end date is on or after enrollment date

Table 55: Use of Medications of Interest by Study Day, Actual Disease Severity, and Treatment Group – As Treated Population

Study Day	Baricitinib + RDV (N=X)				Placebo + RDV (N=X)				All Subjects (N=X)			
	Moderate (N=X)		Severe (N=X)		Moderate (N=X)		Severe (N=X)		Moderate (N=X)		Severe (N=X)	
	n	%	n	%	n	%	n	%	n	%	n	%
Any Medication of Interest												
Day 1	x	Xx	x	xx	x	xx	x	xx	x	xx	x	xx
Day 3	x	Xx	x	xx	x	xx	x	xx	x	xx	x	xx
Day 5	x	Xx	x	xx	x	xx	x	xx	x	xx	x	xx
Day 8	x	Xx	x	xx	x	xx	x	xx	x	xx	x	xx
Day 11	x	Xx	x	xx	x	xx	x	xx	x	xx	x	xx
...Repeat for all categories and sub-categories of the medications in Section 6.4												
N = Number of subjects in the As Treated Population. n=Number of subjects reporting taking at least one prohibited medication by the specified study day.												

Programming Note: If the start date of the prohibited medication is on or before the specified (actual) study day, then the subject will be denoted as taking the med for that Study Day.

Table 56: Overall Summary of Adverse Events – As Treated Population

Subjects ^a with	Baricitinib + RDV (N=X)						Placebo + RDV (N=X)						All Subjects (N=X)					
	Moderate (N=X)		Severe (N=X)		Any Severity (N=X)		Moderate (N=X)		Severe (N=X)		Any Severity (N=X)		Moderate (N=X)		Severe (N=X)		Any Severity (N=X)	
	N	%	n	%	n	%	n	%	n	%	n	%	n	%	n	%	n	%
At least one adverse event	X	x	x	x	x	x	x	x	x	x	x	x	x	x	x	x	x	X
At least one Severe or Life-threatening (Grade 3 or 4) adverse event	X	x	x	x	x	x	x	x	x	x	x	x	x	x	x	x	x	X
At least one related adverse event	X	x	x	x	x	x	x	x	x	x	x	x	x	x	x	x	x	X
Moderate (Grade 2)	X	x	x	x	x	x	x	x	x	x	x	x	x	x	x	x	x	X
Severe (Grade 3)	X	x	x	x	x	x	x	x	x	x	x	x	x	x	x	x	x	X
Life-threatening (Grade 4)	X	x	x	x	x	x	x	x	x	x	x	x	x	x	x	x	x	X
Severe or Life-Threatening (Grade 3 or 4)	X	x	x	x	x	x	x	x	x	x	x	x	x	x	x	x	x	X
Death (Grade 5)	X	x	x	x	x	x	x	x	x	x	x	x	x	x	x	x	x	X
At least one not related adverse event	X	x	x	x	x	x	x	x	x	x	x	x	x	x	x	x	x	X
Moderate (Grade 2)	X	x	x	x	x	x	x	x	x	x	x	x	x	x	x	x	x	X
Severe (Grade 3)	X	x	x	x	x	x	x	x	x	x	x	x	x	x	x	x	x	X
Life-threatening (Grade 4)	X	x	x	x	x	x	x	x	x	x	x	x	x	x	x	x	x	X
Death (Grade 5)	X	x	x	x	x	x	x	x	x	x	x	x	x	x	x	x	x	X
At least one serious adverse event	X	x	x	x	x	x	x	x	x	x	x	x	x	x	x	x	x	X
At least one serious adverse event with fatal outcome	X	x	x	x	x	x	x	x	x	x	x	x	x	x	x	x	x	X
At least one related serious adverse event	X	x	x	x	x	x	x	x	x	x	x	x	x	x	x	x	x	X
At least one related serious adverse event with fatal outcome	X	x	x	x	x	x	x	x	x	x	x	x	x	x	x	x	x	X
At least one adverse event leading to study drug discontinuation	X	x	x	x	x	x	x	x	x	x	x	x	x	x	x	x	x	X
At least one related adverse event leading to study drug discontinuation	X	x	x	x	x	x	x	x	x	x	x	x	x	x	x	x	x	X

Subjects ^a with	Baricitinib + RDV (N=X)						Placebo + RDV (N=X)						All Subjects (N=X)					
	Moderate (N=X)		Severe (N=X)		Any Severity (N=X)		Moderate (N=X)		Severe (N=X)		Any Severity (N=X)		Moderate (N=X)		Severe (N=X)		Any Severity (N=X)	
	N	%	n	%	n	%	n	%	n	%	n	%	n	%	n	%	n	%
At least one adverse event leading to early termination ^b	X	x	x	x	x	x	x	x	x	x	x	x	x	x	x	x	x	X
At least one Unanticipated Problem	X	x	x	x	x	x	x	x	x	x	x	x	x	x	x	x	x	X

N = Number of subjects in the actual disease severity stratum and As Treated Population
^aSubjects are counted once for each category regardless of the number of events.
^bAs reported on the Adverse Event eCRF.
 All Grade 3 and 4 AEs are captured as AEs. In addition, any Grade 2 or higher suspected drug-related hypersensitivity reaction is reported as an AE.

Programming Note: Use actual severity

Table 57: Subject-Level Rates of Adverse Events and Differences between Treatment Groups – As Treated Population

	Baricitinib + RDV (N=X)		Placebo + RDV (N=X)		Risk Difference (95% CI)
	n	%	n	%	
Subjects ^a with at least one:					
AE	x	x	x	x	x.x (x.x, x.x)
Related AE	x	x	x	x	x.x (x.x, x.x)
Grade 3-4 AE	x	x	x	x	x.x (x.x, x.x)
Grade 3-4 Related AE	x	x	x	x	x.x (x.x, x.x)
SAE	x	x	x	x	x.x (x.x, x.x)
Related SAE	x	x	x	x	x.x (x.x, x.x)
SAE with fatal outcome	x	x	x	x	x.x (x.x, x.x)
Related SAE with fatal outcome	x	x	x	x	x.x (x.x, x.x)
AE leading to discontinuation of study drug	x	x	x	x	x.x (x.x, x.x)
Related AE leading to discontinuation of study drug	x	x	x	x	x.x (x.x, x.x)
N = Number of subjects in the As Treated Population.					
^a Subjects are counted once for each category regardless of the number of events.					

Table 58: Adverse Events Occurring in 5% of Subjects in Any Treatment Group by MedDRA System Organ Class and Preferred Term, and Treatment Group - As Treated Population

Preferred Term	MedDRA System Organ Class	Baricitinib + RDV (N=X)			Placebo + RDV (N=X)			All Subjects (N=X)		
		n	%	Events	n	%	Events	n	%	Events
PT1	SOC1	x	x	x	x	x	x	x	x	x
Etc.	Etc.	x	x	x	x	x	x	x	x	x

N = number of subjects in the As Treated Population (number of subjects at risk).
n = number of subjects reporting event.
Events = total frequency of events reported.

Programming Notes:

Select all preferred terms/System organ classes where the % for any treatment group or overall is >= 5%.
Sort preferred terms by descending order of frequency.

Tables with similar format:

Table 59: Adverse Events Occurring in 5% of Subjects in Any Treatment Group by MedDRA System Organ Class and Preferred Term, and Treatment Group – Moderate Disease Severity, As Treated Population

Table 60: Adverse Events Occurring in 5% of Subjects in Any Treatment Group by MedDRA System Organ Class and Preferred Term, and Treatment Group – Severe Disease Severity, As Treated Population

Programming Notes for Tables 59 and 60: Actual disease severity will be used.

Table 61: Treatment-Emergent Renal Adverse Events by Preferred Term and Treatment Group – As Treated Population

Preferred Term	Baricitinib + RDV (N=X)			Placebo + RDV (N=X)			All Subjects (N=X)		
	n	%	Events	n	%	Events	n	%	Events
Any treatment-emergent hepatic adverse event	x	x	x	x	x	x	x	x	x
Glomerular filtration rate decreased	x	x	x	x	x	x	x	x	x
Blood creatinine increased	x	x	x	x	x	x	x	x	x
Acute kidney injury	x	x	x	x	x	x	x	x	x
Creatinine renal clearance decreased	x	x	x	x	x	x	x	x	x
Renal failure	x	x	x	x	x	x	x	x	x
Renal impairment	x	x	x	x	x	x	x	x	x
Proteinuria	x	x	x	x	x	x	x	x	x
Renal tubular necrosis	x	x	x	x	x	x	x	x	x
Blood creatinine abnormal	x	x	x	x	x	x	x	x	x
Continuous haemodiafiltration	x	x	x	x	x	x	x	x	x
Glomerular filtration rate abnormal	x	x	x	x	x	x	x	x	x

N = Number of subjects in the As Treated Population.
n = Number of subjects reporting event.
Events = Total frequency of events reported.

Table with similar format:

Table 62: Treatment-Emergent Hepatic Adverse Events by Preferred Term and Treatment Group – As Treated Population

Table 63: Related Adverse Events by MedDRA System Organ Class and Preferred Term, and Treatment Group - As Treated Population

MedDRA System Organ Class	Preferred Term	Baricitinib + RDV (N=X)			Placebo + RDV (N=X)			All Subjects (N=X)		
		n	%	Events	n	%	Events	n	%	Events
Any SOC	Any PT	x	x	x	x	x	x	x	x	x
SOC1	Any PT	x	x	x	x	x	x	x	x	x
Etc.	Etc.

N = number of subjects in the As Treated Population (number of subjects at risk).
n = number of subjects reporting event.
Events = total frequency of events reported.

Table 64: Deaths by Day 15 or Day 29 by Treatment Group and Randomized Disease Severity – ITT Population

Study Day	Randomized Disease Severity	Baricitinib + RDV (N=X)			Placebo + RDV (N=X)		
		n	Mortality Rate ^a	Rate 95% CI	n	Mortality Rate ^a	Rate 95% CI
Day 15	Moderate	X	x.x	x.x, x.x	x	x.x	x.x, x.x
	Severe	X	x.x	x.x, x.x	x	x.x	x.x, x.x
	Any Severity	X	x.x	x.x, x.x	x	x.x	x.x, x.x
Day 29	Moderate	X	x.x	x.x, x.x	x	x.x	x.x, x.x
	Severe	X	x.x	x.x, x.x	x	x.x	x.x, x.x
	Any Severity	X	x.x	x.x, x.x	x	x.x	x.x, x.x

N = Number of Subject in the specified treatment group and analysis population.
n = Number of subjects in a given treatment group who died by the given timepoint
^a Mortality Rate is the Kaplan-Meier estimate.

Tables with similar format:

Table 65: Deaths by Day 15 or Day 29 by Treatment Group and Actual Disease Severity – As Treated Population

Table 66: Time to Death through Day 15 and 29 by Treatment Group and Randomized Disease Severity – ITT Population

Study Day	Treatment Group	Randomized Disease Severity	n	Median Time		HR		P-value
				Estimate	95% CI	Estimate	95% CI	
Day 15	Baricitinib + RDV (N=X)	Moderate	x	x.x	x.x, x.x	x.xx	x.xx, x.xx	--
	Placebo + RDV (N=X)		x	x.x	x.x, x.x			
	Baricitinib + RDV (N=X)	Severe	x	x.x	x.x, x.x	x.xx	x.xx, x.xx	--
	Placebo + RDV (N=X)		x	x.x	x.x, x.x			
	Baricitinib + RDV (N=X)	Any Severity	x	x.x	x.x, x.x	x.xx	x.xx, x.xx	x.xxx
	Placebo + RDV (N=X)		x	x.x	x.x, x.x			
Day 29	Baricitinib + RDV (N=X)	Moderate	x	x.x	x.x, x.x	x.xx	x.xx, x.xx	--
	Placebo + RDV (N=X)		x	x.x	x.x, x.x			
	Baricitinib + RDV (N=X)	Severe	x	x.x	x.x, x.x	x.xx	x.xx, x.xx	--
	Placebo + RDV (N=X)		x	x.x	x.x, x.x			
	Baricitinib + RDV (N=X)	Any Severity	x	x.x	x.x, x.x	x.xx	x.xx, x.xx	x.xxx
	Placebo + RDV (N=X)		x	x.x	x.x, x.x			

N= Number of subjects in the specified treatment group and analysis population.

n = Number of subjects who died by the specified study day.

HR is the ratio of the hazard of Death in each treatment group estimated from the stratified Cox model. The ratio is Baricitinib + RDV to Placebo + RDV.

P-value calculated using the stratified Log-rank test.

Tables with similar format:

Table 67: Time to Death through Day 15 and 29 by Treatment Group and Actual Disease Severity – As Treated Population

Table 68: Time to Death through Day 15 and 29 by Treatment Group within Subgroups – ITT Population

Table 69: Time to Death through Day 15 and 29 by Treatment Group: Medications of Interest Sensitivity Analysis – ITT Population

Table 70: Time to Death through Day 15 and 29 by Treatment Group: Interaction Modeling – ITT Population

Programming notes for Table 68:

Log-rank p-values will not be included in this table so the column will be removed. The Disease Severity column will be removed and to the left of the Study Day column, a column titled “Analysis/Subgroup” will be inserted. Rows will be generated for each subgroup.

Programming notes for Table 69:

Log-rank p-values will not be included in this table so the column will be removed. The table will include a column to the left of the “n” column titled “m”. The corresponding footnote will read “m = Number of subjects reporting use of the medication of interest.” The Disease Severity column will be removed and a “Medication of Interest” column will be inserted to the left of Study Day. Separate models will be fit for the following categories of medications (see Section 6.4):

- Any Medication of Interest
- Hydroxychloroquine/Chloroquine
- Corticosteroids
- Anti-Inflammatory Drugs

The table will include the following footnote: “In this analysis, subjects that reported use of the specified medications of interest (Section 6.4 of the SAP) are censored at time of medication receipt.”

Programming notes for Table 70:

This table will only include the Treatment Group and HR columns only as well as a column to the left of Treatment Group titled “Interaction”. Two models will be run: “Treatment – Randomized Disease Severity” will include a treatment*randomized disease severity interaction term. “Treatment – Baseline Ordinal Score” will include a treatment*baseline ordinal score interaction term. For each interaction model, the p-value for the interaction term will be provided in a footnote reading “The p-value for the treatment by [randomized disease severity/baseline ordinal score] interaction term was 0.xxxx.”.

Table 71: Time to Death through Day 15 and 29 by Treatment Group: Restricted Mean Survival Time Analysis – ITT Population

Study Day	Treatment Group	Randomized Disease Severity	n	Restricted Mean Recovery Time		Difference	
				Estimate	95% CI	Estimate	95% CI
Day 15	Baricitinib + RDV (N=X)	Moderate	x	x.X	x.X, x.X	x.XX	x.XX, x.XX
	Placebo + RDV (N=X)		x	x.X	x.X, x.X		
	Baricitinib + RDV (N=X)	Severe	x	x.X	x.X, x.X	x.XX	x.XX, x.XX
	Placebo + RDV (N=X)		x	x.X	x.X, x.X		
	Baricitinib + RDV (N=X)	Any Severity	x	x.X	x.X, x.X	x.XX	x.XX, x.XX
	Placebo + RDV (N=X)		x	x.X	x.X, x.X		
Day 29	Baricitinib + RDV (N=X)	Moderate	x	x.X	x.X, x.X	x.XX	x.XX, x.XX
	Placebo + RDV (N=X)		x	x.X	x.X, x.X		
	Baricitinib + RDV (N=X)	Severe	x	x.X	x.X, x.X	x.XX	x.XX, x.XX
	Placebo + RDV (N=X)		x	x.X	x.X, x.X		
	Baricitinib + RDV (N=X)	Any Severity	x	x.X	x.X, x.X	x.XX	x.XX, x.XX
	Placebo + RDV (N=X)		x	x.X	x.X, x.X		

N= Number of subjects in the specified treatment group, disease severity, and analysis population.

n = Number of subjects who died by the specified study day.

Difference is the difference in the restricted mean mortality time between Baricitinib + RDV and Placebo + RDV.

Table 72: Subjects Experiencing Grade 3 or 4 AEs and SAEs through Day 29 by Treatment Group and Actual Disease Severity – As Treated Population

Safety Event Outcome	Baricitinib + RDV			Placebo + RDV			P-value
	n	%	95% CI	n	%	95% CI	
Any Severity (N = X)							
Grade 3 or 4 AE	x	x	x.x, x.x	x	x	x.x, x.x	0.xxx
SAE	x	x	x.x, x.x	x	x	x.x, x.x	0.xxx
Moderate (N = X)							
Grade 3 or 4 AE	x	x	x.x, x.x	x	x	x.x, x.x	0.xxx
SAE	x	x	x.x, x.x	x	x	x.x, x.x	0.xxx
Severe (N = X)							
Grade 3 or 4 AE	x	x	x.x, x.x	x	x	x.x, x.x	0.xxx
SAE	x	x	x.x, x.x	x	x	x.x, x.x	0.xxx
N = Number of Subject in the As Treated Population and specified actual disease severity stratum. n = Number of subjects in a given treatment group who experienced the specified safety event outcome. 95% CI calculated using C-P/Blaker method P-value calculated using Barnard's Exact Test							

Table 73: Analysis of Time to Death, SAEs, or Grade 3 or 4 AEs by Treatment Group – As Treated Population

Actual Disease Severity	Treatment Group	n	Median Time		HR		P-value
			Estimate	95% CI	Estimate	95% CI	
Any Severity (N=X)	Baricitinib + RDV (N=X)	X	x.x	x.x, x.x	x.xx	x.xx, x.xx	x.xxx
	Placebo + RDV (N=X)	X	x.x	x.x, x.x			
Moderate (N=X)	Baricitinib + RDV (N=X)	X	x.x	x.x, x.x	x.xx	x.xx, x.xx	--
	Placebo + RDV (N=X)	X	x.x	x.x, x.x			
Severe (N=X)	Baricitinib + RDV (N=X)	X	x.x	x.x, x.x	x.xx	x.xx, x.xx	--
	Placebo + RDV (N=X)	X	x.x	x.x, x.x			

N= Number of subjects in the As Treated Population and specified actual disease severity stratum.

n = Number of subjects who died or experienced SAEs or Grade 3 or 4 AEs.

HR is the ratio of the hazard of Death/SAE/AE of Grade 3 or 4 in each treatment group estimated from the stratified Cox model. The ratio is Baricitinib + RDV to Placebo + RDV. P-value calculated using the Log-rank test

Table 74: Infections by Treatment Group – As Treated Population, Moderate Disease Severity

Anatomical Location	Pathogen	Baricitinib + RDV (N=X)									Placebo + RDV (N=X)								
		Severe			Life-Threatening			Death			Severe			Life-Threatening			Death		
		n	%	Events	n	%	Events	n	%	Events	n	%	Events	n	%	Events	n	%	Events
Any Location	Any Pathogen	x	x	x	x	x	X	x	x	x	x	x	x	x	x	x	x	x	x
Location 1	Any Pathogen	x	x	x	x	x	X	x	x	x	x	x	x	x	x	x	x	x	x
	Pathogen 1	x	x	x	x	x	X	x	x	x	x	x	x	x	x	x	x	x	x
	Pathogen 2	x	x	x	x	x	X	x	x	x	x	x	x	x	x	x	x	x	x
Location 2	Any Pathogen	x	x	x	x	x	X	x	x	x	x	x	x	x	x	x	x	x	x
	Pathogen 1	x	x	x	x	x	X	x	x	x	x	x	x	x	x	x	x	x	x
	Pathogen 2	x	x	x	x	x	X	x	x	x	x	x	x	x	x	x	x	x	x

Note: Percents may not add to 100 because participants may have infections with multiple pathogens. All Grade 3 or 4 infections are also reported as AEs.
 N=Number of participants randomized to Treatment group.
 n=Number of participants with infection.

Tables with similar format:

Table 75: Opportunistic Infections by Treatment Group – As Treated Population, Moderate Disease Severity

Table 76: Infections by Treatment Group – As Treated Population, Severe Disease Severity

Table 77: Opportunistic Infections by Treatment Group – As Treated Population, Severe Disease Severity

Table 78: Infections by Treatment Group – As Treated Population, All Subjects

Table 79: Opportunistic Infections by Treatment Group – As Treated Population, All Subjects

Programming Notes for Table 75, Table 77, Table 79: Opportunistic infections will be identified by the sponsor and will be documented in a spreadsheet/SAS dataset to be imported into ADaM dataset programming.

Table 80: Abnormal Laboratory Results of Grade 3 or 4 by Parameter, Maximum Severity, Time Point, and Treatment Group – As Treated Population

Laboratory Parameter	Time Point	Treatment Group	N	Severe/ Grade 3		Life Threatening/ Grade 4		Severe/Grade 3 or Life Threatening/Grade 4	
				n	%	n	%	n	%
Any Parameter	Baseline	Baricitinib + RDV	x	x	x	x	x	x	x
		Placebo + RDV	x	x	X	x	x	x	x
	Day 3	Baricitinib + RDV	x	x	X	x	x	x	x
		Placebo + RDV	x	x	X	x	x	x	x
	Day 5	Baricitinib + RDV	x	x	X	x	x	x	x
		Placebo + RDV	x	x	X	x	x	x	x
	Day 8	Baricitinib + RDV	x	x	X	x	x	x	x
		Placebo + RDV	x	x	X	x	x	x	x
	Day 11	Baricitinib + RDV	x	x	X	x	x	x	x
		Placebo + RDV	x	x	X	x	x	x	x
	Day 15	Baricitinib + RDV	x	x	X	x	x	x	x
		Placebo + RDV	x	x	X	x	x	x	x
	Day 29	Baricitinib + RDV	x	x	X	x	x	x	x
		Placebo + RDV	x	x	X	x	x	x	x
	Maximum Severity Post Baseline	Baricitinib + RDV	x	x	X	x	x	x	x
		Placebo + RDV	x	x	X	x	x	x	x

Each parameter will be summarized individually similar to the above...

The “Max Post Baseline” rows indicate the maximum severity experienced by each subject at any time point post baseline, including unscheduled assessments and assessments beyond Day 29.
N = Number of subjects in the As Treated Population

Programming Note: D-dimer and CRP results are not included in this table. Include all lab parameters that are being graded in this table.

Tables with similar format:

Table 81: Abnormal Laboratory Results of Grade 3 or 4 by Parameter, Maximum Severity, Time Point, and Treatment Group – Moderate Disease Severity, As Treated Population

Table 82: Abnormal Laboratory Results of Grade 3 or 4 by Parameter, Maximum Severity, Time Point, and Treatment Group – Severe Disease Severity, As Treated Population

Programming Notes for Table 81 and Table 82: Actual Disease Severity will be used. Include all lab parameters that are being graded in this table.

Table 83: Treatment-Emergent Laboratory Abnormalities - As Treated Population

Laboratory Parameter	Grade	Baricitinib + RDV (N=X)			Placebo + RDV (N=X)		
		N	n	%	N	n	%
Any Parameter	1	x	x	x	x	x	x
	2	x	x	X	x	x	x
	3	x	x	X	x	x	x
	4	x	x	X	x	x	x
	Any Grade	x	x	X	x	x	x

Continue for all graded parameters

N = number of subjects in the As Treated Population with any post-baseline data available for the specified Lab Parameter.
 n = number of subjects in the As Treated Population with treatment emergent abnormalities for the specified Lab Parameter.
 A treatment emergent laboratory abnormality is defined as a post-baseline abnormal value with a severity grade greater than at baseline.

Table 84: Summary Statistics of Laboratory Results by Parameter, Study Visit Day, and Treatment Group – As Treated Population

Laboratory Parameter	Study Visit Day	Treatment Group	Absolute					Change from Baseline				
			N	Mean	SD	Median	Min, Max	N	Mean	SD	Median	Min, Max
Parameter 1	Baseline	Baricitinib + RDV	x	xx.x	xx.x	xx.x	xx.x, xx.x	---	---	---	---	---
		Placebo + RDV	x	xx.x	xx.x	xx.x	xx.x, xx.x	---	---	---	---	---
	Day 3	Baricitinib + RDV	x	xx.x	xx.x	xx.x	xx.x, xx.x	x	xx.x	xx.x	xx.x	xx.x, xx.x
		Placebo + RDV	x	xx.x	xx.x	xx.x	xx.x, xx.x	x	xx.x	xx.x	xx.x	xx.x, xx.x
	Day 5	Baricitinib + RDV	x	xx.x	xx.x	xx.x	xx.x, xx.x	x	xx.x	xx.x	xx.x	xx.x, xx.x
		Placebo + RDV	x	xx.x	xx.x	xx.x	xx.x, xx.x	x	xx.x	xx.x	xx.x	xx.x, xx.x
	Day 8	Baricitinib + RDV	x	xx.x	xx.x	xx.x	xx.x, xx.x	x	xx.x	xx.x	xx.x	xx.x, xx.x
		Placebo + RDV	x	xx.x	xx.x	xx.x	xx.x, xx.x	x	xx.x	xx.x	xx.x	xx.x, xx.x
	Day 11	Baricitinib + RDV	x	xx.x	xx.x	xx.x	xx.x, xx.x	x	xx.x	xx.x	xx.x	xx.x, xx.x
		Placebo + RDV	x	xx.x	xx.x	xx.x	xx.x, xx.x	x	xx.x	xx.x	xx.x	xx.x, xx.x
	Day 15	Baricitinib + RDV	x	xx.x	xx.x	xx.x	xx.x, xx.x	x	xx.x	xx.x	xx.x	xx.x, xx.x
		Placebo + RDV	x	xx.x	xx.x	xx.x	xx.x, xx.x	x	xx.x	xx.x	xx.x	xx.x, xx.x
	Day 29	Baricitinib + RDV	x	xx.x	xx.x	xx.x	xx.x, xx.x	x	xx.x	xx.x	xx.x	xx.x, xx.x
		Placebo + RDV	x	xx.x	xx.x	xx.x	xx.x, xx.x	x	xx.x	xx.x	xx.x	xx.x, xx.x

Continue for all parameters...

N = Number of subjects in the As Treated Population with laboratory data available for the parameter at the specified study visit.

Programming Notes: Include all lab parameters in this table.

Tables with similar format:

Table 85: Summary Statistics of Laboratory Results by Parameter, Study Visit Day, and Treatment Group – Moderate Disease Severity, As Treated Population

Table 86: Summary Statistics of Laboratory Results by Parameter, Study Visit Day, and Treatment Group – Severe Disease Severity, As Treated Population

Programming Notes for Tables 85 and 86: Actual Disease Severity will be used. Include all lab parameters in this table.

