6. GENERAL STATISTICAL CONSIDERATIONS

6.1. General Principles

This is a double-blind, placebo controlled randomized trial with a two-sided type I error rate of 0.05. Secondary hypotheses have been ordered according to relative importance. These will be described according to the appropriate summary statistics, e.g.

- Percentages/proportions/odds ratios for categorical data. For tabular summaries of percentages/proportions, the denominator (e.g. number of subjects with non-missing data) will be displayed.
- Means, median, and range for continuous data, median for time-to-event data.

Confidence intervals will be generated; for the primary analysis, the confidence level will take into account the group-sequential design of the trial (see Section 6.6 and Section 8.1) whereas 95% confidence intervals will be generated for secondary and exploratory outcomes. For hazard ratio and odds ratio estimates, Wald confidence intervals will be used. For other efficacy outcomes, Wilson or Score confidence intervals will be used. For safety outcomes, exact (e.g. Clopper-Pearson) confidence intervals will be used.

When calculating treatment effects (e.g. differences, hazard ratios, odds ratios) and when using treatment arm as a covariate in regression modeling, the remdesivir+placebo arm will be used as the reference group. For regression modeling that uses strata variables defined in Section 6.4, the first stratum listed for each variable in that section will be used as the reference group.

For the final time-to-event analyses, the following SAS pseudocode will be used to perform stratified analyses to generate stratum-specific median time to event estimates and confidence intervals, stratum-specific Kaplan-Meier curves, and to perform the log-rank test. For any unstratified analyses, code can be used after the removal of the `strata ... ;` line.

```
proc lifetest data=dataset plots=(s);
  time TimeVariable * CensorVariable(1);
  strata StrataVariable;
  test TreatmentVariable;
run;
```

Note that the interim efficacy analyses will be performed using R. For all interim and final analyses, the software used will calculate the log rank statistic using the formula in Section 8.1.1.

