8.1.2. Supplemental and Sensitivity Analyses

For all supplemental and sensitivity analyses of the primary outcome, p-values may or may not be reported, and 95% confidence levels will be used for confidence interval estimates.

The primary analysis will be repeated in the As Treated analysis population where subjects who are not treated will be censored at enrollment. The tabular and graphical summaries described in the previous section will be replicated for this As Treated analysis.

Sensitivity analyses will be performed using Cox proportional hazards models to estimate the hazard ratio. First, an ITT analysis will be performed in which subjects who die prior to recovering are treated as experiencing a competing risk in the Fine-Gray proportional hazards regression model. Second, a Cox model will be fit with binary indicators for treatment group and disease severity Moderate vs. Severe [separate models for randomized stratum and actual stratum] as well as a treatment * disease severity interaction term. The models will be fit to the ITT analysis population. The treatment group hazard ratios and CIs will be reported for both sets of models and the interaction term p-value will be reported for the interaction models. As requested by the DSMB, a restricted mean survival time analysis will be performed as an exploratory analysis. The restricted mean recovery time estimates will be provided for each treatment group and randomized disease severity stratum as well as the difference in restricted mean recovery time between treatment groups within each of the severity strata (Table 18). Time to recovery will also be explored within prior Remdesivir treatment subgroups (Any Treatment vs. No Treatment) (Table 19).

The primary analysis will also be repeated using the other subgroups defined in Section 6.4 in place of disease severity. Each subgroup will be considered separately and the tabular and graphical summaries described in the previous section will be replicated for each subgroup. The tabular summary will also include results from an analysis of time to recovery controlling for age

and duration of symptoms as continuous covariates and baseline d-dimer and CRP values as continuous covariates. A forest plot will be generated to display the overall treatment hazard ratio estimate and CI from each of the within-stratum analyses (Table 20 and Table 21). These analyses will be performed in the ITT and As Treated populations.

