ITT Population	Baricitinib + RDV (N=X)	Moderate	x	x.x	x.x, x.x	x.xx	x.xx, x.xx
	Placebo + RDV (N=X)		x	x.x	x.x, x.x		
	Baricitinib + RDV (N=X)	Severe	x	x.x	x.x, x.x	x.xx	x.xx, x.xx
	Placebo + RDV (N=X)		x	x.x	x.x, x.x		
	Baricitinib + RDV (N=X)	Any Severity	x	x.x	x.x, x.x	x.xx	x.xx, x.xx
	Placebo + RDV (N=X)		x	x.x	x.x, x.x		

Repeat for the As Treated Population.

N= Number of subjects in the specified treatment group, disease severity, and analysis population.

n = Number of recovered subjects.

Difference is the difference in the restricted mean recovery time between Baricitinib + RDV and Placebo + RDV.

Programming Notes:

Within a severity stratum:

```
proc lifetest data=enrevent plots=(rmst) method=breslow rmst(cl);
by stratum;
time evntday * Censor(1);
strata trtcode /diff=all;
ods output rmst=rmst;
run;
```

Stratified by disease severity (“Any Severity” row).

```
proc lifetest data=enrevent plots=(rmst) method=breslow rmst(cl);
time evntday * Censor(1);
strata trtcode CRSEVERE /diff=all;
ods output rmst=rmst;
run;
```

Table 19: Time to Recovery by Treatment Group within Prior RDV Treatment Subgroups

Analysis Population	Treatment Group	Prior RDV Treatment Subgroup	n	Median Time to Recovery		HR	
				Estimate	95% CI	Estimate	95% CI
ITT Population	Baricitinib + RDV (N=X)	No Prior Treatment	x	x.x	x.x, x.x	x.xx	x.xx, x.xx
	Placebo + RDV (N=X)		x	x.x	x.x, x.x		
	Baricitinib + RDV (N=X)	Any Prior Treatment	x	x.x	x.x, x.x	x.xx	x.xx, x.xx
	Placebo + RDV (N=X)		x	x.x	x.x, x.x		

Repeat for the As Treated Population.

N= Number of subjects in the specified treatment group, disease severity, and analysis population.

n = Number of recovered subjects.

HR is the ratio of the hazard of recovery in each treatment group estimated from the Cox model. The ratio is Baricitinib + RDV to Placebo + RDV.

Additional tables with similar format as Table 15:

Table 20: Time to Recovery by Treatment Group within Subgroups – ITT Population

Table 21: Time to Recovery by Treatment Group within Subgroups – As Treated Population

Table 22: Time to Recovery by Treatment Group and Randomized Disease Severity: Readmittance Sensitivity Analysis – ITT Population

Table 23: Time to Recovery by Treatment Group and Randomized Disease Severity: Medications of Interest Sensitivity Analysis – ITT Population

Programming Notes for Tables 20 and 21:

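### SAP Table 18's code for the Any Severity row returns treatment-by-severity contrasts instead of the overall treatment difference, and the table's time horizon is not stated

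*SAP*

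**What the plan says.** SAP Section 8.1.2 states that, at the DSMB's request, "a restricted mean survival time analysis will be performed as an exploratory analysis". It commits to restricted means by arm and randomized severity stratum, and to the "difference in restricted mean recovery time between treatment groups within each of the severity strata (Table 18"). It does not mention an overall difference and names no horizon.

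The Table 18 shell in SAP Appendix 1 goes further. It has Moderate, Severe and Any Severity rows, each with one mean per arm and one difference with a confidence interval. The footnote reads: "Difference is the difference in the restricted mean recovery time between Baricitinib + RDV and Placebo + RDV".

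The programming notes give two code blocks. Both open with "proc lifetest data=enrevent plots=(rmst) method=breslow rmst(cl", followed only by the closing bracket and semicolon. The first runs separately by severity stratum and uses "strata trtcode /diff=all". The second is headed "Stratified by disease severity", is assigned to the Any Severity row, drops the by-stratum run and uses "strata trtcode CRSEVERE /diff=all".

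On follow-up, SAP Section 3.3.2 measures time in days from randomization. It censors deaths before recovery at 28 days and completers who have not recovered at the day of their Day 29 visit. The schedule in protocol Appendix B, Section 1.2, allows that visit a window of ±3 days.

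**The concern.** The second block is meant to fill a row that holds one treatment comparison across severities. As written, it treats severity as a further grouping factor to be compared, not as a factor to adjust for. The row would then have no matching output, and a programmer would have to choose a method when the table is produced, possibly after unblinding.

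The horizon raises a separate question. A restricted mean is defined only up to a truncation time, and a longer horizon gives a different quantity. If the plan does not fix it, the estimand depends on when the last visits happened to fall.

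**Working it through.** **What the strata statement does.** I take this from the SAP itself.
- In the within-stratum block of Table 18, treatment alone is in the strata statement and severity is handled by the by-stratum run. The variable in the strata statement therefore defines the groups that are differenced.
- In the stratified log-rank code of SAP Section 6.1, the strata line is "strata StrataVariable". Treatment is kept out of it and compared through a separate test statement.

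Under either usage, putting both variables in the strata statement makes every treatment-by-severity cell a group.

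**Counting.** Groups: 2 arms × 2 severities = 4. Pairwise contrasts: 4 × 3 / 2 = 6.
- Two are treatment contrasts within moderate and within severe disease, which the first block already gives.
- Two compare moderate with severe within one arm.
- Two change arm and severity together.

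No contrast is the overall treatment difference, and no group is a whole arm.

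**Illustration.** The plan states no restricted mean, so there is no figure to reproduce. I use the recovery rate ratio of 1.25 from SAP Section 5. The other inputs are my assumptions: exponential recovery, and 28-day control recovery of 85% (moderate) and 50% (severe). With rate λ and horizon τ, the restricted mean is (1 - exp(-λτ))/λ. At τ = 28:

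| Group | λ per day | Restricted mean (days) |
|---|---|---|
| Control, moderate | -ln(0.15)/28 = 0.0678 | 12.55 |
| Treated, moderate | 1.25 × 0.0678 = 0.0847 | 10.71 |
| Control, severe | -ln(0.50)/28 = 0.0248 | 20.20 |
| Treated, severe | 1.25 × 0.0248 = 0.0309 | 18.73 |

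The six contrasts are -1.84 (moderate), -1.47 (severe), and four cross-severity values: -6.18, -7.65, -8.02 and -9.49. With half the patients moderate, the wanted overall value is about 0.5 × (-1.84) + 0.5 × (-1.47) = -1.65 days. It is not among the six.

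**Choice of combination rule.** I simulated one data set with N = 1032 (SAP Section 5), 1:1 allocation, the same rates, severe disease with probability 0.4, visits at 25 to 31 days and no deaths. At τ = 28 the severity-weighted difference was -1.28 days and the pooled unstratified difference -1.38 days. One data set shows only that the two rules need not agree.

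**Horizon.** SAP Section 3.3.2 censors deaths at 28 days, and Section 8.1.1 describes the same censoring as Day 29, so Day 29 is 28 elapsed days. A visit on Days 26 to 32 is then 25 to 31 elapsed days. In the half-moderate case the overall difference is -1.45, -1.65 and -1.85 days at τ = 25, 28 and 31. I then varied the moderate share from 30% to 70% and control recovery between 85%/50% and 80%/60%:

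| τ (days) | Overall difference (days) |
|---|---|
| 25 | -1.36 to -1.58 |
| 28 | -1.58 to -1.80 |
| 31 | -1.80 to -2.01 |

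**The case against.** The strongest reply is that little depends on this block. Section 8.1.2 promises only within-stratum differences, and the first block delivers them. A reader might infer that the analysis the DSMB asked for would not be delivered, but the documents do not support that. Only the overall row, which appears in the table shell and not in the body text, is left without output.

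It can also be said that the second block saves its results to a dataset, and that two of its six contrasts are exactly what a weighted overall difference needs. That is true, but no weights or variance rule are stated anywhere. Table 15, by contrast, says that its Any Severity hazard ratio comes from the stratified Cox model. SAP Section 15 says that fine detail of newly added outputs was not necessarily carried into the body, so the shell code is the only specification for this row.

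On the horizon, SAP Section 3.2 describes the endpoint as censored at Day 29 and Section 8.1.1 compares arms through Day 29, which suggests that 28 days was intended. But Section 3.3.2 uses the actual visit day. The cap at actual Day 29 that Section 3.3.10 applies to time to death is not applied to recovery.

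**Conclusion.** The point holds. The code written for the Any Severity row of Table 18 gives four group means and six contrasts, none of which is what the row and its footnote report. This is stated code with the wrong output, not missing detail. It rests on reading the strata statement as the SAP uses it elsewhere.

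The unstated horizon is a second, smaller gap. Under the assumptions above, moving it by 3 days either way from 28 shifts the overall difference by about 0.2 day.

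Three stronger readings should be avoided.
- The missing horizon does not by itself prevent a difference from being computed; the crossing of treatment with severity is the defect.
- One might infer that the rows will use different horizons, or that follow-up runs to 32 days. The first depends on a software default that the documents do not give. The second mixes study days with elapsed days: the excess over 28 is at most about 3 days.
- Table 71 (mortality) cannot be charged with the same fault. It names Day 15 and Day 29 and has no code block.

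The analysis is exploratory, and the primary stratified log-rank test is untouched. This is a minor correction.

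**What to change.** 1. Replace the Any Severity code in Table 18 by one of two stated methods:
   - the overall difference as w₁d₁ + w₂d₂, where d₁ and d₂ are the two stratum-specific differences and the weights are fixed in advance (for example, stratum share), with variance w₁²·Var(d₁) + w₂²·Var(d₂) and per-arm means weighted the same way; or
   - a comparison on treatment alone, labelled as unstratified.
2. Set one horizon for every row of Table 18, in both code blocks and in Section 8.1.2. Twenty-eight days from randomization is a natural choice: it matches the death-censoring day, and beyond it the censored deaths have left the risk set.
3. Add a sentence to Section 8.1.2 that the table also gives an overall difference, and name the method in the footnote.
4. In Table 71, keep the Day 15 and Day 29 horizons and state the same combination rule for its Any Severity rows.

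The cost is a few lines of code and two sentences of text, best settled before unblinding. No new data are needed.
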